14.7 Dose Modification (Extension Cohorts)

Reduction/interruption of dosing for adverse events may take place at any time during the study according to guidelines in [Table 3](#). Dose reductions should occur in increments of 200 mg/day, depending on the toxicity grade, as noted in [Table 3](#). Dose reduction/interruption guidelines for hematologic and nonhematologic treatment-related TEAEs are based on severity. Dose interruptions can be implemented at the discretion of the treating Investigator to manage intolerable or clinically significant toxicity. If a dose interruption is required, study assessments should be performed as scheduled, irrespective of the study drug delay, with the exception of PK assessments, which should be deferred until treatment is resumed. Interruptions due to toxicity

lasting >3 weeks require treatment discontinuation unless the medical monitor approves continuation.

Table 3: Dose Modifications

Event	Severity	Pexidartinib Dosage Modifications
Hepatotoxicity		
Increased ALT and/or AST	>3 to 5 × ULN	Withhold and monitor liver tests weekly. If AST and ALT ≤3 × ULN within 4 weeks, resume at reduced dose. If AST or ALT not ≤3 × ULN in 4 weeks, permanently discontinue pexidartinib.
	>5 to 10 × ULN	Withhold and monitor liver tests twice weekly. If AST and ALT ≤3 × ULN within 4 weeks, resume at reduced dose. If AST or ALT not ≤3 × ULN in 4 weeks, permanently discontinue pexidartinib.
	>10 × ULN	Permanently discontinue pexidartinib. Monitor liver tests twice weekly until AST or ALT ≤5 × ULN, then weekly until ≤3 × ULN.
Increased ALP ^a and GGT	ALP >2 × ULN with reflex test of GGT >2 × ULN	Permanently discontinue pexidartinib. Monitor liver tests including GGT twice weekly until ALP ≤5 times ULN, then weekly until ≤2 × ULN.
Increased bilirubin	TB >ULN to <2 × ULN or DB >ULN and <1.5 × ULN	Withhold and monitor liver tests twice weekly. If an alternate cause for increased bilirubin is confirmed and bilirubin <ULN within 4 weeks, resume at reduced dose. If bilirubin not <ULN in 4 weeks, permanently discontinue pexidartinib.
	TB ≥2 × ULN or DB >1.5 × ULN	Permanently discontinue pexidartinib. Monitor liver tests twice weekly until bilirubin ≤ULN.
Adverse Reactions or Other Laboratory Abnormalities		
Any	Severe or intolerable	Withhold until improvement or resolution. Resume at a reduced dose upon improvement or resolution.

ALT = alanine aminotransferase; ALP = alkaline phosphatase; AST = aspartate aminotransferase;

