DB = direct bilirubin; GGT = gamma-glutamyl transferase; TB = total bilirubin; ULN = upper limit of normal

^a Confirm ALP elevations as liver isozyme fraction.

Dose interruptions for Grade 2 non-hematologic toxicity for up to 1 week can be implemented at the discretion of the treating physician to manage intolerable or clinically significant toxicity. No dose reduction is required when resuming treatment.

Liver enzyme abnormalities, including increased transaminase values, have occurred with pexidartinib and should also be managed as described in [Table 4](#).

Re-challenge with a reduced dose of pexidartinib may result in a recurrence of increased serum transaminases, bilirubin, or ALP. Monitor liver tests weekly for the first month after re-challenge.

Table 4: Additional Liver Evaluation

Evaluation	Comments
Increase frequency of testing liver chemistries to twice per week (if Grade 3+), including INR, and continue until liver chemistries have stabilized, and then reduce to weekly until liver chemistries return to normal or baseline.	Investigational treatment may be started after liver function tests recover to Grade 0 to 1 or baseline level, and in consultation with Medical Monitor.
Detailed history focusing on medications and substances used: alcohol, change in medication dosages, new medications added, attention to use of acetaminophen, OTC medication use, and recreational drug use. Check for change in diet or use of dietary supplements, with particular attention to dose and duration of any herbal product.	Suspect medications will be discontinued or substituted for if possible.
Detailed medical history and physical examination seeking new abnormalities.	Evaluate abnormalities found.
Full serological evaluation for hepatitis A, B, C, and E (IgG and IgM). Check for autoimmune hepatitis with serological laboratory studies.	If viral hepatitis or autoimmune hepatitis suggested, have patient evaluated by hepatologist.
Liver ultrasound performed to evaluate liver and biliary tree.	Evaluate any abnormalities found.
Check history for exposure to chemical agents.	Remove chemical exposure and have patient seen by hepatologist.
Obtain hepatology consult if liver function continues to rise beyond 14 days.	Contact Medical Monitor.
We request that cases be discussed with the Medical Monitor as defined in the protocol whenever investigational product is being held for liver function test abnormality.	

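### Table 3's >10 × ULN row ends twice-weekly liver tests once either transaminase is ≤5 × ULN, so a plateau above 10 × ULN may be tested less often than one at 7 × ULN

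*Combined protocol and SAP*

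**What the plan says.** Section 14.7 covers the extension cohorts. The transaminase rows of Table 3 carry the label "Increased ALT and/or AST", so either enzyme alone is enough to place a patient in a row.

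- **>5 to 10 × ULN row:** "Withhold and monitor liver tests twice weekly. If AST and ALT ≤3 × ULN within 4 weeks, resume at reduced dose". If that is not met, "If AST or ALT not ≤3 × ULN in 4 weeks, permanently discontinue pexidartinib". The row contains no step-down to weekly testing.
- **>10 × ULN row:** drug is stopped permanently, and follow-up is: "Monitor liver tests twice weekly until AST or ALT ≤5 × ULN, then weekly until ≤3 × ULN".

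The text before Table 4 says that liver enzyme abnormalities "should also be managed as described in" that table, so both tables apply. The first row of Table 4 reads: "Increase frequency of testing liver chemistries to twice per week (if Grade 3+), including INR, and continue until liver chemistries have stabilized". After that it reduces testing to weekly until values are normal or at baseline. The protocol neither defines stabilization nor sets a level above which it cannot be declared.

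**The concern.** The two lower transaminase rows use their connectives consistently: recovery needs both enzymes, and failure needs only one. The step-down in the >10 × ULN row is a recovery condition, yet it is written with *or*. A patient with ALT 12 × and AST 4 × meets it from the first day, because AST was never above 5 ×. The second step, down to ≤3 × ULN, names no enzyme at all.

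The result could be that the most severe transaminase row gets lighter follow-up than the row above it. What is at stake is how soon a change is seen in a patient with marked liver injury, for example a rise in bilirubin that would point to cholestatic injury. The gap between tests is about 3.5 days on twice-weekly testing (7 ÷ 2) and 7 days on weekly testing. The patient is already off drug, so continued exposure is not the issue.

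**Working it through.** The plan gives no figure of its own here. The check applies the two tables as written to example patients and counts liver panels over the first four weeks.

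**Inputs**

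- Row entry: either enzyme (Table 3 event label).
- Table 3, >10 × ULN: 2 panels a week until AST *or* ALT is ≤5 × ULN, then 1 a week.
- Table 3, >5 to 10 × ULN: 2 panels a week up to the 4-week decision.
- Table 4: 2 panels a week for Grade 3+ until stabilized, then 1 a week.
- Assumptions: ALT and AST stay flat; stabilization is declared at the end of week *k*; where the tables differ, the stricter frequency applies; the Grade 3 cut-off is below 12 × ULN. The documents print only that Grade 2 or higher means >3 × ULN (extension flow chart, footnote 5; Attachment 1). Any Grade 3 cut-off from 5 × to just under 12 × gives the same result for ALT 12 ×.

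**Rules applied to each patient**

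| ALT / AST (× ULN) | Table 3 as written | Table 3 with *and* | Table 4 before / after stabilization |
|---|---|---|---|
| 12 / 4 | weekly at once | twice weekly | twice weekly / weekly |
| 7 / 4 | twice weekly | twice weekly | twice weekly / weekly |
| 12 / 6 | twice weekly | twice weekly | twice weekly / weekly |

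The 12 / 6 patient shows that the problem needs a discordant pair: one enzyme above 10 × and the other at or below 5 ×. The Table 4 entry for the 7 × patient assumes a Grade 3 cut-off below 7 ×, but nothing turns on it, because Table 3 alone keeps that patient on twice weekly.

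**Panels in weeks 1 to 4**

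Panels in a week = max(Table 3 frequency, Table 4 frequency).

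- 12 / 4 as written: 2 a week for *k* weeks, then 1 a week for 4 − *k* weeks, so 2*k* + (4 − *k*) = 4 + *k*.
- 12 / 4 with *and*: 2 × 4 = 8.
- 7 / 4: 2 × 4 = 8.

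| Stabilized after week *k* | 12 / 4 as written | 12 / 4 with *and* | 7 / 4 | Shortfall, 8 − (4 + *k*) |
|---|---|---|---|---|
| 1 | 5 | 8 | 8 | 3 |
| 2 | 6 | 8 | 8 | 2 |
| 3 | 7 | 8 | 8 | 1 |
| 4 | 8 | 8 | 8 | 0 |

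Before stabilization Table 4 holds both patients at twice weekly, so there is no shortfall then. After it, both tables allow weekly testing at 12 / 4, while Table 3 still requires twice weekly at 7 / 4.

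**The case against.** The strongest reply is that *AST or ALT* is shorthand for whichever enzyme was raised. It follows a label that admits either enzyme, and *until* suggests a high value coming down. On the literal reading, Table 3's twice-weekly instruction would never start for the 12 / 4 patient, and a reading that empties an instruction is usually the wrong one. A careful investigator would probably follow the intended sense. This is a fair point, but the text does not say it. It also leaves a case open: if both enzymes were above 10 × and AST falls to 5 × while ALT stays at 11 ×, both were raised and one now meets the condition.

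Second, the gap opens only if someone calls a transaminase of 12 × ULN stabilized, in a patient with discordant enzymes and a flat course. That is a narrow set of circumstances, and the documents give no frequency for it. This stands, and it is why the point is small.

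Third, the two rows serve different purposes. The >5 to 10 × row is a hold-and-decide row limited to four weeks and states no test frequency afterwards; the >10 × row is a follow-up schedule. The comparison therefore holds only between stabilization and week 4. This also stands.

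Fourth, there are other safeguards. Section 18.0 allows extra safety evaluations at the investigator's discretion, Attachment 1 asks for close follow-up above 3 × ULN, and Section 26.2 requires drug-related events to be followed until they subside or return to baseline. If bilirubin also meets one of its rows in Table 3, twice-weekly testing applies anyway. These make harm less likely, but the general provisions set no test frequency. Table 4's hepatology consult is triggered by continuing rise beyond 14 days, which a plateau does not show.

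**Conclusion.** The concern holds as a minor wording error in an operative safety rule. As written, and once chemistries are called stabilized, a patient with ALT 12 × / AST 4 × may be tested weekly while one with ALT 7 × / AST 4 × must still be tested twice weekly until the 4-week decision. The size is 3, 2, 1 or 0 panels per affected patient in the first four weeks, for stabilization after 1, 2, 3 or 4 weeks.

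This rests on the literal reading of *or*, a steady discordant plateau, and a declaration of stabilization at a high level. That onset is covered rests on a Grade 3 cut-off below 12 × ULN, which is very likely but not printed. No dosing rule, stopping rule, endpoint or analysis is affected.

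**What to change.** In the >10 × ULN transaminase row of Table 3, change the follow-up to: *twice weekly until AST and ALT are both ≤5 × ULN, then weekly until both are ≤3 × ULN*. The 12 × / 4 × patient then stays on twice-weekly testing whether or not the values are called stabilized, and the inversion disappears.

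Add one sentence to Section 14.7: where Tables 3 and 4 differ, the stricter test frequency and the longer follow-up apply. This partly restates that both tables apply, but it also settles whether weekly testing ends at ≤3 × ULN (Table 3) or at normal or baseline (Table 4).

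The cost is two wording changes and the added sentence. For patients above 10 × ULN whose other enzyme is ≤5 × ULN, correcting the step-down adds 0 to 3 panels in the first four weeks, then about one a week while the plateau lasts.

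### Section 14.7's Grade 2 sentence allows full-dose resumption after ALT/AST of >3 to 5 × ULN, where Table 3 requires a reduced dose; no sentence says which rule prevails

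*Combined protocol and SAP*

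**What the plan says.** Section 14.7 (Dose Modification, Extension Cohorts) contains four relevant pieces of text.

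- **Opening paragraph.** It begins "Reduction/interruption of dosing for adverse events may take place at any time during the study according to guidelines in" Table 3, and sets the step size: "Dose reductions should occur in increments of 200 mg/day, depending on the toxicity grade".
- **Table 3, ALT/AST >3 to 5 × ULN.** The drug is withheld and liver tests are repeated weekly. Then: "If AST and ALT ≤3 × ULN within 4 weeks, resume at reduced dose". Where recovery does not come in time, the row ends treatment: "If AST or ALT not ≤3 × ULN in 4 weeks, permanently discontinue pexidartinib".
- **Paragraph after Table 3.** "Dose interruptions for Grade 2 non-hematologic toxicity for up to 1 week can be implemented at the discretion of the treating physician", for toxicity that is intolerable or clinically significant. It ends "No dose reduction is required when resuming treatment".
- **Table 4 (Additional Liver Evaluation).** Beside the item on testing frequency it comments: "Investigational treatment may be started after liver function tests recover to Grade 0 to 1 or baseline level, and in consultation with Medical Monitor".

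On grading, footnote 5 of the extension-cohort flow chart and Attachment 1 (Liver Effect Biomarkers) both put the start of Grade 2 ALT or AST elevation at >3 × ULN. The extension dose is 1000 mg/day (Synopsis, Dosage and Regimen; section 9.1).

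**The concern.** Raised transaminases are a non-hematologic toxicity, and by the protocol's own threshold a value just above 3 × ULN is Grade 2. The general Grade 2 sentence therefore reaches an event that already has its own, stricter row in Table 3, and nothing in the sentence takes liver tests out. A site relying on it could treat the hold as optional and return the patient to full dose, and would then be in breach of Table 3.

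The stakes are in patient safety rather than inference. Section 14.7 itself warns that "Re-challenge with a reduced dose of pexidartinib may result in a recurrence of increased serum transaminases, bilirubin, or ALP", so even the reduced dose is regarded as carrying risk. The dose after a liver signal should not depend on which paragraph a site reads.

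Table 4 raises a lesser version of the same question. Its restart comment gives no dose and does not set aside the events after which Table 3 stops treatment for good.

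**Working it through.** The plan states no figure to reproduce. The check compares the rules and then does one piece of dose arithmetic.

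**Step 1: is ALT/AST of >3 to 5 × ULN Grade 2 in this protocol?** The lower bound is explicit (footnote 5 and Attachment 1: >3 × ULN). The upper bound is inferred: Table 4 ties twice-weekly testing to Grade 3 and above, and Table 3 begins twice-weekly testing at >5 × ULN. Together these place >3 to 5 × ULN in Grade 2.

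**Step 2: the two rules for that range.**

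| | Table 3 | Sentence after Table 3 |
|---|---|---|
| Hold | Required | At the physician's discretion |
| Length | Up to 4 weeks, then permanent stop | Up to 1 week |
| Recovery level | AST and ALT ≤3 × ULN | None named |
| Dose on resuming | Reduced | No reduction required |
| Liver tests | Named | Neither named nor excluded |

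**Step 3: size of the difference in dose.** Inputs are 1000 mg/day and a step of 200 mg/day. Table 3 does not say how many steps make a reduced dose, so one step is an assumption.

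- One step: 1000 − 200 = 800 mg/day; 1000/800 = 1.25, so full dose is 25% higher.
- Two steps, to show the range: 1000 − 2 × 200 = 600 mg/day; 1000/600 = 1.67, or 67% higher.
- A patient on the renal-impairment dose (14.7.1, 600 mg/day), one step: 600 − 200 = 400 mg/day; 600/400 = 1.50, or 50% higher.

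These are ratios of daily dose. They are not estimates of exposure or of liver risk.

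**Step 4: Table 4's restart comment against Table 3's six hepatotoxicity rows** (three ALT/AST, one ALP with GGT, two bilirubin).

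- *ALT/AST >3 to 5 and >5 to 10 × ULN.* Since Grade 2 starts above 3 × ULN, recovery to Grade 0 to 1 is the same as ≤3 × ULN. The thresholds agree; Table 4 is silent only on dose and on the 4-week limit.
- *Lower bilirubin row.* Table 3 asks for a confirmed alternate cause and bilirubin below ULN. Table 4 repeats neither condition.
- *Three rows with a permanent stop at onset* (ALT/AST >10 × ULN; ALP >2 × ULN with GGT >2 × ULN; TB ≥2 × ULN or DB >1.5 × ULN). Table 4 does not exclude them.

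**Step 5: is precedence stated?** Four cues favour Table 3: the opening sentence ties dosing changes to it, liver abnormalities are to be managed *also* by Table 4, Table 4's title calls it additional evaluation, and re-challenge is described as being at a reduced dose. None of them says that Table 3 prevails or that liver events fall outside the Grade 2 sentence.

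**The case against.** The best answer is that the text can be read without conflict. Table 3 has one block for hepatotoxicity and another for other adverse reactions and laboratory abnormalities. The Grade 2 sentence speaks of intolerable toxicity, which echoes the single row of the second block, so it can be taken as relaxing that row for non-liver events. The next paragraph then turns to liver enzymes as a separate subject. The sentence is also permissive: a site that follows Table 3 complies with both texts, and going wrong means passing over an exact row in favour of a general sentence. This is probably what the sponsor intended. It lessens the conflict without removing it, because a literal reader finds no liver exclusion.

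A reader might infer three stronger things that the documents do not support.

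- *That Table 4 overrides Table 3's permanent stops.* The comment says only that treatment may be started, and it requires consultation with the Medical Monitor. Table 4's last row speaks of product being held, which suggests that the table addresses holds. What remains is silence on the permanent-stop events, not an instruction to restart after them.
- *That the two tables disagree across the ALT/AST range.* For >3 to 10 × ULN the Grade 0 to 1 threshold matches Table 3.
- *That Table 4 creates the difficulty for patients with liver metastases.* Inclusion criterion 9 admits them at <5 × ULN, so someone entering above 3 × ULN is in Table 3's hold range before any rise on drug. The gap is that Table 3 makes no allowance for baseline.

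The size in step 3 is also fairly challenged: it rests on an assumed number of steps, and the documents give no count of patients affected.

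**Conclusion.** The point holds as a conflict of wording in 14.7. For ALT/AST of >3 to 5 × ULN, the sentence after Table 3, taken literally, permits a discretionary hold and resumption at 1000 mg/day where Table 3 requires a hold and gives 800 mg/day. The 800 mg/day figure assumes one 200 mg/day step, and placing the range in Grade 2 rests on the protocol's own thresholds. Table 4's failure to exclude Table 3's permanent-stop events is secondary, and the Medical Monitor's involvement limits it further. Table 3 very likely governs both, but that is inference from the wording. No sample size, power or error rate changes, and the documents do not allow the number of patients affected to be estimated. A correction is worthwhile because the looser reading gives the higher dose after a liver signal and the remedy is small.

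**What to change.** Add to section 14.7, by amendment:

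1. The Grade 2 interruption sentence does not apply to liver-test abnormalities listed in Table 3.
2. For those abnormalities, Table 3 governs withholding, restart, dose and permanent discontinuation.
3. Table 4's restart comment applies only where Table 3 permits resumption, and at Table 3's reduced dose.

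The cost is a few sentences, with no new procedures, patients or eligibility change. Sites and the Medical Monitor lose the looser reading for liver events listed in Table 3 only. The exclusion should not be widened to all liver tests: Table 3 has no row for an isolated GGT rise or for ALP elevation with GGT ≤2 × ULN, and the existing discretion there should stay.

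Two minor omissions are separate and for the sponsor to settle. Table 3 makes no allowance for patients with liver metastases who enter at >3 to <5 × ULN; without liver metastases, entry is capped at 2.5 × ULN and the question does not arise. Table 2 (section 12.1, CYP3A and UGT inhibitors) starts at 800 mg/day, so it lists no dose for a patient on 1000 mg/day who cannot avoid an inhibitor.

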14.7.1 Renal Impairment

A reduced dose of 600 mg/day (200 mg in the morning and 400 mg in the evening) is recommended in study subjects with mild to severe renal impairment (creatinine clearance [CL_{cr}] 15 to 89 mL/min estimated by Cockcroft-Gault using actual body weight).

14.8 End of Study/Early Withdrawal (last dose for subjects that enroll in phase 4 continuation study or immediately transition to commercial pexidartinib; last + 30 ± 7 days for all other subjects)

Note: In order to be eligible to participate in the phase 4 PVNS continuation study, subjects must not be withdrawn from PLX108-01 until they are ready to begin screening in the phase 4 continuation study. Screening for the phase 4 continuation study may occur prior to withdrawal from PLX108-01.

Following the last dose of drug, all patients will have the following evaluations:

1. Physical examination including weight (kg) and vital signs (sitting blood pressure, pulse rate, and respiratory rate, and oral temperature [°F]).
2. Standard 12-lead ECG to determine QTcF.
3. Clinical laboratory evaluation (hematology, chemistry, urinalysis, serum pregnancy test (women of child-bearing potential).
4. ECOG Performance status assessment.
5. For patients enrolled after the implementation of Amendment 8, collect the six (6) completed NRS for PVNS Symptoms questionnaires and give the patient another one of the questionnaires to complete predose. NOTE: the NRS for PVNS Symptoms questionnaire to be completed in the clinic is exactly the same as the other 6 daily questionnaires.
6. For patients enrolled after the implementation of Amendment 8, then give the patient the Western Ontario and McMaster Universities Osteoarthritis Index (WOMAC) questionnaire to complete predose. NOTE: At each of the applicable visits, sites should refrain from providing any interpretation of how the questions should be answered by the patient.
7. Radiographic assessment of tumor burden.
8. Test article compliance.
9. Concomitant medications.
10. Collection of surgical data - If surgical resection of the tumor is performed within 30 days of the last dose of study treatment, details of the surgery and its outcome should be obtained.

14.9 Twelve-week Follow-up (last dose + 12 weeks [+4-week window])

Within +12 weeks (+4 week window) of the last dose of study drug, all patients that don't enroll in the phase 4 continuation study or transition immediately to commercial pexidartinib will have the following study evaluations:

1. Radiographic assessment of tumor burden
2. Collection of surgical data - If surgical resection of the tumor is performed within 12 weeks of the last dose of study treatment, details of the surgery and its outcome should be obtained.

For patients who miss the 30-day and 12-week post-treatment follow-up visit, post-treatment radiographic assessments from any source (e.g., primary care provider) within 24 weeks of last dose are acceptable.

